9.2.5. Inclusion criteria

A subject will be included in the Registry if all of the following criteria are met:

- Exposure to vaccine occurs during pregnancy or within 28 days preceding conception.
- Subject is a US resident.
- A HCP is identified (name, address and phone number).
- Subject can be identified (by GSK or HCP).

Data from registered subjects will be included in the analyses if the following criterion is met:

- Pregnancy is ongoing and the outcome is unknown.

9.2.6. Exclusion criterion

Data from registered subjects will not be included in the analyses if the following criterion is met:

- Outcome of pregnancy is known at the time of initial report. Types of known outcomes include prenatal testing reports in which the results are abnormal or outside the reference range, indicating possible abnormality in the fetus. Typically, pregnancies > 16 weeks gestation will have undergone prenatal testing that can identify whether a child has congenital abnormalities.

9.3. Variables

9.3.1. Primary endpoint

- Occurrence of any abnormal pregnancy outcomes in women intentionally or unintentionally vaccinated with *Boostrix* during pregnancy or within 28 days preceding conception.

9.3.2. Data to be collected (Amended 05 October 2017)

Initial and follow-up data will be collected using questionnaires. *Data for enrollment will be collected using the Initial Notification Form. Follow-up of cases is performed within 2 months of the estimated date of delivery (EDD) to ascertain pregnancy outcome (through the Pregnancy Outcome Form) and approximately 6 months and 12 months after the EDD (for all live births for whom the contact details of their HCP will be available) to ascertain the presence of birth defects not diagnosed before (through the 6- and 12-month post-delivery Follow-Up Form).* The following data will be collected:

- Patient identifier.
- Maternal data, including date of birth, date of last menstrual period (LMP), EDD.
- Maternal relevant medical/family history.
- Paternal relevant medical/family history.
- Type of conception.
- Prenatal testing.
- Maternal prenatal drug/vaccine exposure, including drug/vaccine name, date of administration, route of administration, dose, lot number, indication.
- Pregnancy outcome.
- Method of delivery.
- Infant/fetal information, including gestational weeks at birth/miscarriage/termination, gender, length, weight, Apgar score.
- Description of birth defects, if applicable.
- AEs experienced by the fetus/infant or the mother.
- Reporter information.
- Any additional data that seems relevant for this study.

9.4. Data sources (Amended on 05 October 2017)

Reporting of vaccine-exposed pregnancies to the Registry is voluntary. Registration can be initiated from a HCP or from a consumer, in which case permission is requested to obtain confirmation and follow-up from their HCP. ***Follow-up from the HCP of the infant post birth 6 and 12 months will be performed when the contact details are available and with consumer's permission.*** A toll-free telephone number for reporting AEs and vaccine-exposed pregnancies to the Registry is listed in the product information leaflet and on the GSK Registry website. Retrospective post-marketing reports and relevant scientific publications are potential sources of supplementary information.

9.5. Study size

No minimum sample size is required for this descriptive study.

Refer to Section 9.2.1.2 for the size of the potential “at-risk” population and the number of pregnant vaccinees.

9.6. Data management

9.6.1. Data collection (Amended on 05 October 2017)

Initial and follow-up data will be collected using questionnaires. Initial data will be collected before the outcome is known. Follow-up of cases will be performed at the following timepoints:

- ***For consumer reports:***
 - ***At initial notification of pregnancy exposure: 2 attempts at 4-6 week intervals will be made to obtain more information about the pregnancy (e.g. estimated time of delivery (EDD) and/or last menstrual period (LMP) and to obtain permission to contact the patient's HCP***
 - ***Within 2 months after EDD, 1 additional attempt is made if permission to contact the patient's HCP has not already been granted to obtain more information about the pregnancy and obtain the permission to contact the patient's HCP.***
 - ***Within 2 months after EDD (and if the patient has not previously provided the contact information for the infant's HCP): 2 attempts at 4-6 week intervals will be made for the prospective cases reporting a live birth to obtain the contact information of the HCP supervising the health of the infant.***

- ***For the HCP reports:***
 - ***At initial notification of pregnancy exposure or once permission has been granted for reports initially received from a consumer, two attempts at 4-6 week intervals will be made to obtain more information via pregnancy follow-up form.***
 - Within 2 months of the EDD, to ascertain outcome. ***Two follow-up*** attempts to obtain outcome information will be made before any case is considered lost to follow-up.
- An additional follow-up ***attempt*** will be done for ***the*** live births approximately 6 months and 12 months after the EDD to ascertain the presence of birth defects not diagnosed at the time of the initial ***pregnancy outcome***. ***This follow-up will be done for the prospective reports if the consumer has granted the permission and when the contact details of the HCP attending the infant are available.***

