9.6.2.1. Solicitation of outcome (Amended on 05 October 2017)

As explained in section 9.6.1, within ***two*** months after the EDD and if the HCP has not already provided the ***pregnancy*** outcome, she/he is sent an outcome form (questionnaire). The mode of communication is ***generally via standard letter***.

Two attempts are made to secure the outcome information from the HCP ***via standard letter***. ***For the live births*** and with the mother's permission, attempts are made to solicit information from the pediatrician and/or other specialists who have provided healthcare/consultation to the child ***until 12 months of age***.

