According to the initial version of the protocol, additional follow-up questionnaires should be sent for all live births approximately 6 months and 12 months after EDD to ascertain the presence of birth defects not diagnosed at the time of the initial follow up. However neither of these follow-up questionnaires were implemented as of this protocol amendment.

GSK Biologicals acknowledges the importance of this information and intends to implement both 6- and 12-month follow-up attempts prospectively. The data collection form for 6- and 12-month follow-ups will be developed in parallel to this protocol amendment. For the subjects already enrolled, there will be no attempt to collect the 6 and 12-month data as the likelihood of having appropriate contact details and/or receiving reliable data is low and such practice is likely to introduce recall bias, hence compromising the validity of the results.

Hence, the above proposed changes will only be applicable for patients to be enrolled after the approval of this protocol amendment (and the related documents/forms) when the pregnancy outcome is a live birth, the contact details of the HCP attending the infant are available and with the consumer's permission.

Originally, a signed consent form from pregnant subjects was only requested when these registered themselves into the registry, and to allow GSK to contact their HCPs. GSK will now also encourage HCPs who register their patients to provide these with the consent form. This consent will also allow to contact the HCP supervising the health of the infant up until 12 months after delivery (the updated consent form will now request contact information from HCP supervising the health of infant). This new consent form will be implemented for all prospective reports after the protocol amendment approval.

Gestational age cut-off for spontaneous abortions and stillbirths:

The 20 weeks' cut-off in gestational age has been replaced by 22 weeks based on WHO-ICD 10 noted in the EMA Guideline on pregnancy exposure [EMA, 2006], as per the standard definition used by GSK Biologicals. It is recognized that national regulations might be different.

Exclusion Criteria section:

The following sentence have been deleted from the exclusion criteria section
“Pregnancies in which prenatal testing indicates a normal pregnancy would also be excluded because inclusion of such pregnancies could potentially bias results toward a lower overall estimate of risk for defects”

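### Under 9.6.1, a consumer-reported live birth first learned more than two months after the EDD triggers no request for the infant's HCP details, so its 6- and 12-month birth-defect checks can be missed

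*Combined protocol and SAP*

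**What the plan says.** Section 9.6.1 (Data collection), under consumer reports, sets the timing of the requests for the infant's HCP as "Within 2 months after EDD (and if the patient has not previously provided the contact information for the infant's HCP"). Within that frame, "2 attempts at 4-6 week intervals will be made for the prospective cases reporting a live birth to obtain the contact information". Three conditions therefore apply together: the two-month window, a reported live birth, and details not already supplied.

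The outcome is sought over the same period. For HCP reports, 9.6.1 has "Within 2 months of the EDD, to ascertain outcome", and two "attempts to obtain outcome information will be made before any case is considered lost to follow-up". Section 9.6.2.1 (Solicitation of outcome) sends the outcome form within two "months after the EDD and if the HCP has not already provided the" outcome, and adds that "Two attempts are made to secure the outcome information from the HCP". Neither section says when in the two months the first letter goes, how far apart the letters are, or when the search for an outcome closes.

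The later infant enquiries depend on the requests succeeding: 9.6.1 allows them, with permission, "when the contact details of the HCP attending the infant are available". Annex 4 gives an earlier route to the same details: "the updated consent form will now request contact information from HCP supervising the health of infant".

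**The concern.** Two steps that must run one after the other share one calendar window. The mother is asked for the infant's HCP only once a live birth is reported, but the report may come from an outcome letter that can go out on the last day of that window, with a second letter still to follow. No rule covers a live birth that becomes known after the window has closed.

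At stake is the completeness of the birth-defect count. The 6- and 12-month forms are the stated means of finding defects not diagnosed at the time of the outcome. Under section 9.7 the risk is infants with defects divided by all infants with and without defects, so a live-born infant whose outcome arrived late is still counted below the line. If that infant's later diagnoses are not solicited, the observed risk can only fall, and it is this risk that is set against external background rates. Whether an infant is followed would also depend on how quickly the mother's HCP answered a letter. Section 9.9 discusses pregnancies with no outcome, but not incomplete infant follow-up after a reported live birth.

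**Working it through.** The plan gives no figure of its own to reproduce. The check is calendar arithmetic.

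**Inputs from the protocol.** Window for the requests: two months after the EDD, *W* = 59 to 62 days, with 61 used below (9.6.1). Two requests, spacing *g* = 28 to 42 days (9.6.1). Outcome form sent at any time up to two months after the EDD, two attempts, no closing date (9.6.1, 9.6.2.1).

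**Assumptions, not in the documents.** A reply arrives 7 to 28 days after a letter. The second outcome letter follows the first by 28 to 42 days. The first request to the mother goes out on day *r*, the day the live birth is reported.

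**Step 1: what the window governs.** The first consumer bullet in 9.6.1 has the same form: a time point (initial notification), then two attempts 4-6 weeks apart. Both attempts cannot happen at initial notification, so the opening phrase there can only mark the start of a sequence. Read the same way, the disputed bullet requires *r* ≤ *W*, and the second request may fall later.

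**Step 2: number of requests on that reading.** Two if *r* ≤ 61, none if *r* > 61.

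| First outcome letter (day) | Reply to first letter (day) | Requests | Reply to second letter (day) | Requests |
|---|---|---|---|---|
| 0 | 7–28 | 2 | 35–70 | 2 up to day 61, otherwise 0 |
| 14 | 21–42 | 2 | 49–84 | 2 up to day 61, otherwise 0 |
| 30 | 37–58 | 2 | 65–100 | 0 |
| 61 | 68–89 | 0 | 96–131 | 0 |

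Reply to first letter = letter day + 7 to 28. Reply to second letter = letter day + 28 to 42 + 7 to 28. The last row is the extreme case that 9.6.2.1 permits: every reply falls outside the window.

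**Step 3: the stricter reading, for comparison.** If both requests had to fall inside the window, the condition would be *r* ≤ *W* − *g*. That is 61 − 42 = day 19 to 61 − 28 = day 33 (over *W* = 59 to 62, day 17 to day 34). A birth learned after that and by day 61 would get one request. After day 61 both readings give none.

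**Step 4: effect on the risk.** Let *d1* be defects known at the outcome, *d2* defects diagnosed later, and *m* the share of infants not followed for this reason. If later defects are spread evenly over followed and unfollowed infants and the rest are fully followed, the observed count is *d1* + (1 − *m*)*d2*. The relative shortfall in risk is then *m* × *d2*/(*d1* + *d2*). The direction is downward; the documents give neither *m* nor *d2*.

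**Step 5: a ceiling on who is exposed.** Annex 4 limits the 6- and 12-month forms to women enrolled after the amendment is approved. Taking the amendment date (05 October 2017) as the approval date and the end of data collection as 2 August 2019 gives about 22 months. At the expected rate of fewer than 100 registrations a year, that is fewer than 100 × 22/12 ≈ 183 registrations. The cases at issue are the subset that are consumer-reported, end in a live birth first learned after two months, and lack earlier details.

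**The case against.** The strongest reply is that the rule is a fallback with a narrow reach. It covers consumer reports only, and only where the mother has not already named the infant's HCP. The updated consent form asks for that name and is to be used for all prospective reports after the amendment. A mother may also report the birth herself, well before any letter to her HCP is answered. Section 9.6.2.1 separately provides, with her permission, for approaching the child's doctors up to 12 months of age, with no two-month limit. And 9.6.1 makes the later forms depend on the details being available, not on when they were obtained. All of this stands. It reduces the number affected and rules out any claim that late outcomes in general lose follow-up.

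A reader might also infer that both requests must fit inside the two months, so that a birth learned after day 19 to 33 gets only one. The wording does not exclude this, but the parallel bullet at initial notification points to the other reading, and percentages built on the stricter one should not be used.

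What the reply does not remove is the case where the other routes have failed and the live birth is learned after two months. The bullet exists for women whom the consent form missed, and for them it gives no instruction. Section 9.6.2.1 permits contact with the child's doctors but does not say how their details are found.

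**Conclusion.** The point holds in a limited form. For a consumer-reported prospective case whose infant-HCP details were not supplied earlier, a live birth first learned after about day 61 (59 to 62, depending on the months) gets no request under 9.6.1 as written. This is so on either reading of the window. Such an infant remains in the denominator without the 6- and 12-month enquiries, unless the details reach the registry some other way, and the birth-defect risk can be biased downward.

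The size is unknown. The documents give no letter dates, reply times or share of women supplying the details early, so any percentage would reflect only the values assumed for them. With fewer than about 183 registrations open to infant follow-up by the end of data collection, on the assumptions above, the number of infants is probably small. The case for change rests on the gap being avoidable at almost no cost. A reader might also infer that the first outcome letter should be fixed at the EDD. No inconsistency in the documents requires that, and the gap closes without it.

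**What to change.** In this bullet of 9.6.1, replace the calendar window with a trigger: *from receipt of a live-birth outcome, whenever received, two attempts 4-6 weeks apart, before the next scheduled infant form (6 or 12 months)*. Keep the existing limit to women who have not already given the details.

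The new rule covers every late reply in the table. The latest, day 131, would give requests on day 131 and on day 159 to 173 (131 + 28 to 42), ahead of a 6-month form at about day 183. For an outcome learned too late for that, the 12-month form becomes the target.

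The cost is one sentence in the protocol and the matching entry in the case-management schedule. The planned number of attempts does not change. The downside is that some cases stay open longer.

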9.6.2. Processing of reports (Amended on 05 October 2017)

Reports are entered into the GSK safety database by ***GSK Case Management Group (CMG)*** using existing mechanisms and practices. Medical Dictionary for Regulatory Activities (MedDRA) is used in the database to code AEs.

Follow-up is conducted by ***CMG***. The HCP is contacted if she/he requests or if initial information is insufficient or needs clarification. ***The follow-up of cases is performed as described in section 9.6.1.***

9.6.2.1. Solicitation of outcome (Amended on 05 October 2017)

As explained in section 9.6.1, within ***two*** months after the EDD and if the HCP has not already provided the ***pregnancy*** outcome, she/he is sent an outcome form (questionnaire). The mode of communication is ***generally via standard letter***.

Two attempts are made to secure the outcome information from the HCP ***via standard letter***. ***For the live births*** and with the mother's permission, attempts are made to solicit information from the pediatrician and/or other specialists who have provided healthcare/consultation to the child ***until 12 months of age***.

9.6.2.2. Classification of outcomes (Amended 05 October 2017)

This Registry uses the term 'birth defects' for outcomes sometimes referred to as 'congenital anomalies'. For purposes of analysis, pregnancy outcomes are dichotomized according to the presence or absence of birth defects. ***Pregnancy outcomes are*** further categorized as: 1) live births, 2) spontaneous abortions (i.e., pregnancy losses), 3) ***Elective/induced abortions*** and 4) ***Fetal deaths/Stillbirths***.

This Registry adopts a definition of a child with a birth defect as any live or stillborn neonate with a structural or chromosomal abnormality diagnosed before 6 years of age. The Registry employs a conservative approach of including all morphologic anomalies, including minor ones, as birth defects.

To provide consistency in the definitions of major defects in this Registry, CDC MACDP criteria are used for the classification of defects [CDC, 2008; Correa-Villasenor, 2003]. Some of the conditions excluded from the MACDP criteria for major structural defects may actually have major clinical, functional, or genetic significance. Therefore, minor malformations not appearing in the CDC inclusion list may be classified as birth defects in this Registry. In addition, CDC guidelines disqualify as defects those findings that are present in infants delivered at less than 36 weeks of gestation and are attributable to prematurity itself, such as a patent ductus arteriosus or inguinal hernias. Infants with infectious conditions (e.g., neonatal sepsis) or isolated biochemical abnormalities (e.g., hyperbilirubinemia) are classified as being without birth defects unless there is a possibility that the condition reflects an unrecognized congenital abnormality. All other congenital abnormalities are included in the 'birth defects' category, regardless of whether the neonate is delivered alive, including structural defects in neonates delivered prior to 20 weeks of gestation or weighing less than 500 g.

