9.7. Data analysis (Amended on 05 October 2017)

Pregnancy outcomes include spontaneous abortion (pregnancy loss before 22 weeks gestation), fetal deaths/stillbirths (loss at or after 22 weeks gestation), elective/*induced* abortions and live births. Gestational weeks are counted from the date of the LMP. The second trimester is considered to begin at week 14 and the third trimester begins at week 28. The presence or absence of birth defects or other abnormalities is evaluated within each of the preceding outcome categories.

Pregnancy outcomes are stratified by the trimester of exposure, with an additional stratum for preconception exposure with no subsequent administration of vaccine during pregnancy. Reports of multiple exposures during a pregnancy (i.e., multiple administrations of *Boostrix*) are classified by the earliest trimester of exposure. When exposure occurs before and after conception, the exposure is classified by the dose administered after conception. The calculations of risk for birth defects are made by dividing the number of infants with birth defects by the total number of infants with and without birth defects. ***Given the descriptive nature of this study, confidence intervals will not be calculated.*** The outcomes of the study will be assessed against known rates from an external reference group for the likelihood of a safety signal warranting further investigation.

The majority of spontaneous abortions occur early in pregnancy [Wilcox, 1981; Wilcox, 1983; Elish, 1996]. If spontaneous abortions were to be evaluated as an outcome of interest, it would be essential to enroll pregnancies as soon as possible after vaccination with *Boostrix*. Because enrollment and recognition of pregnancy would occur at various times, it would be virtually impossible to meaningfully evaluate the effects of *Boostrix* on pregnancy loss [Kennedy, 2004]. Therefore, spontaneous abortions without birth defects are excluded from the risk calculations.

The risk in the general population of all birth defects meeting CDC criteria is approximately 3% (1 of 33) of live births [CDC, 2013b]. The estimated risk cited in the medical literature varies because of differences in case definitions, populations sampled and ascertainment methods. The Collaborative Perinatal Project, using a broader case

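### The planned birth-defect risk matches neither background rate cited in 9.7, and the plan does not say which rate counts as expected

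*Combined protocol and SAP*

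**What the plan says.** **What counts as a defect (9.6.2.2).** A child with a birth defect is defined as "any live or stillborn neonate with a structural or chromosomal abnormality". On minor anomalies the section says: "The Registry employs a conservative approach of including all morphologic anomalies, including minor ones, as birth defects". MACDP criteria are used to classify defects, but the section goes beyond them: "minor malformations not appearing in the CDC inclusion list may be classified as birth defects in this Registry". Findings attributable to prematurity, infections and isolated biochemical abnormalities are set aside, with qualifications. Other congenital abnormalities count "regardless of whether the neonate is delivered alive", including those in deliveries before 20 weeks.

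**How the risk is calculated (9.7).** Infants with defects are divided by all infants, with and without defects. On early losses the section says: "Therefore, spontaneous abortions without birth defects are excluded from the risk calculations". Losses with a reported defect therefore stay in. Section 9.7 also evaluates defects within each outcome category, live births among them. It adds that "confidence intervals will not be calculated".

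**What the risk is set against.** Section 9.7 gives one CDC-criteria rate: "The risk in the general population of all birth defects meeting CDC criteria is approximately 3% (1 of 33) of live births". It then gives 5% to 7% from a project with a broader case definition, without stating the base. Section 9.1.2 offers MACDP as an example of a general-population comparator. Sections 9.2.3 and 9.9 offer the National Birth Defects Prevention Network and the National Center for Health Statistics, also as examples. The first aggregate criterion in 9.7 refers to an expected frequency of defects overall and gives it no value.

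**The concern.** A comparison with an external rate is informative only if both sides count the same events over the same base, or if the difference is stated and allowed for. Here the all-anomaly risk differs from the 3% figure in case definition, and its base is not confined to live births. Its relation to 5% to 7% cannot be judged, because the base of that figure is not given.

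The comparison has a purpose. Sections 9.2.3 and 9.7 commit the Registry to assessing its outcomes against external rates, to see whether a safety signal may need further investigation. With no interval, test or threshold planned, the choice of reference carries much of the weight in how the observed proportion is read. If that choice is left open, the same count can look like an excess or like nothing unusual.

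**Working it through.** **Inputs.** CDC-criteria rate about 3%, or 1 in 33, of live births (9.7). Broader-definition rate 5% to 7%, base not stated (9.7). 391 prospectively reported pregnancies to 2 August 2013 (9.2.1.2). The number of evaluable infants is not in the documents, so 200 and 391 are used only for illustration.

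**The plan's own figure.** 1/33 = 3.03%, which agrees with the stated 3%.

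**Step 1: does any planned quantity line up with 3% of live births?**

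| Quantity | Numerator | Base |
|---|---|---|
| Cited 3% | Defects meeting CDC criteria; whether non-live cases count is not stated | Live births |
| Overall risk in 9.7 | Registry definition, with minor and non-CDC-list anomalies, live and non-live | Infants with and without defects, not confined to live births |
| Live-birth category in 9.7 | Registry definition | Live births |

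The third row fixes the base but keeps the broad numerator. MACDP criteria are applied when defects are classified, but no ratio restricted to them is planned.

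**Step 2: how far apart are the two cited rates?** 5%/3% = 1.67 and 7%/3% = 2.33. Using 1/33 instead gives 1.65 and 2.31. The gap reflects case definition and ascertainment together, and the documents do not separate them.

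**Step 3: expected counts, N × rate.**

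| N (assumed) | at 3% | at 5% | at 7% |
|---|---|---|---|
| 200 | 6.0 | 10.0 | 14.0 |
| 391 | 11.7 | 19.6 | 27.4 |

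**Step 4: what the choice does to one result.** Suppose 20 defects were seen among 391 infants, or 5.1%. Observed over expected is 20/11.73 = 1.71 at 3%, 20/19.55 = 1.02 at 5% and 20/27.37 = 0.73 at 7%.

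**Step 5: how often this would arise at N = 391 (exact binomial).**
- If the Registry definition had a true background of 5% and the vaccine had no effect, the observed proportion would lie above 1/33 with probability 0.976. At 7% the probability exceeds 0.999.
- If the true risk on the Registry ratio were 2/33 = 6.06%, the observed proportion would lie above 5% with probability 0.81 but above 7% with probability only 0.21.

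These are not signal rates, because the plan has no rule that a value above the reference is a signal. They show only that the reading depends on the reference.

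**Step 6: direction of bias.** Minor anomalies and defects in non-live outcomes raise the Registry ratio relative to 3%. Three features lower it: reports with abnormal prenatal tests are excluded (9.2.6), infant follow-up depends on permission and contact details (9.6.1), and 6- and 12-month data will not be sought for women already enrolled (Annex 4). The documents give no sizes for these, so the net direction cannot be determined.

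**The case against.** The strongest defence is that the study is descriptive and open about the problem. Section 9.7 warns: "The estimated risk cited in the medical literature varies because of differences in case definitions, populations sampled and ascertainment methods". It labels each rate with its definition, and 9.9 undertakes to discuss the limits of comparison in the reports. Both rates are written down in advance and both can be shown. The overall frequency is one of three aggregate criteria, beside four for individual cases. Evaluation by outcome category and MACDP classification are already planned, so what is missing is narrow. The sentence in 9.1.2 may also refer to specific defects, which have their own criterion in 9.7.

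Most of this stands, and it limits the weight of the point. It does not remove it: a warning that definitions vary gives no like-for-like ratio, and the overall criterion still has no stated reference.

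A reader might infer more than the documents support:
- That the broad ratio will be judged against 3% alone, or that the benchmark will be picked to suit the data. Nothing says so; the choice is simply left open.
- That the Registry will overstate risk and raise a false signal. Step 6 of the working shows biases in both directions.
- That a CDC-criteria live-birth ratio would match 3% exactly. Section 9.7 gives the denominator of that rate, but not whether non-live cases are in its numerator or up to what age diagnoses count.
- That 9.7 and 9.9 conflict over terminations without a reported defect. Section 9.9 states that exclusion and 9.7 does not contradict it, so any change there is editorial.

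**Conclusion.** The point holds in a limited form. The single overall birth-defect risk in 9.7 is not like-for-like with the 3% rate and is not shown to be like-for-like with 5% to 7%. The first aggregate criterion does not say which rate applies. The open choice spans a factor of 1.7 to 2.3, or about 12 against 20 to 27 expected defects for 391 infants.

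Those counts rest on an assumed number of infants, and no single count is decisive because the plan sets no threshold. The co-primary proportion with any abnormal pregnancy outcome is a separate quantity and is not affected. This should be fixed because the remedy is cheap and uses classifications already in the plan.

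**What to change.** In the protocol:

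1. **Add a ratio to 9.7.** Beside the all-anomaly risk, report live births with CDC/MACDP-criteria defects divided by all live births. Use this ratio, not the all-anomaly risk, for comparison with 3%.
2. **Amend the first aggregate criterion.** Name the reference for each ratio in advance: about 3% for the CDC-criteria live-birth ratio, and 5% to 7% for the all-anomaly risk as the nearest cited context, not shown to be matched.
3. **State the limits of the alignment.** The new ratio agrees with 3% on case criteria and live-birth denominator only. Check in the reference source whether non-live cases are in the numerator and up to what age diagnoses count, and align the Registry numerator if needed. State also that the 9.2.6 exclusion, conditional infant follow-up (9.6.1) and the missing 6- and 12-month data for women already enrolled (Annex 4) can lower the ratio, so a value at or below 3% is not by itself reassuring.
4. **Keep what is there.** Retain the all-anomaly risk and the evaluation by outcome category, so that defects in non-live outcomes stay visible.

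The cost is protocol wording, a check of the reference source and one extra table, with no new data to collect. The new ratio will have fewer events and leaves out defects in non-live outcomes, so it must stand beside the all-anomaly risk and not replace it.
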